8.2.5 Suicidal Ideation and Behavior Risk Monitoring

The C-SSRS is a prospective semi-structured interview comprised of the following areas of assessment: Ideation, Intensity of Ideation, Behavior, and Lethality. It has been used extensively in global clinical studies (academic and industry sponsored) and in a range of therapeutic areas, disorders and indications, including psychiatry, neurology, obesity, urology and endocrinology and is FDA-approved. It has been used to determine eligibility to enroll at screening and at every follow-up visit to prospectively monitor suicidality during the study. The C-SSRS was developed for use in clinical studies and can be administered by non-mental health professionals with training. All C-SSRS raters for this study will have a certificate that verifies training completion and allows them to rate in this study.

Protocol TB006AD2102

Protocol Date and Version: 15 Oct 2021; v 3.0

There are 2 versions of the C-SSRS. The "Past 6 months" version of the C-SSRS will be completed at screening and the "Since Last Visit" version will be completed at all remaining visits according to the SoA (Table 1 and Table 2). The "Since Last Visit" version will also be completed at any unscheduled clinic visits.

8.3 Adverse Events and Serious Adverse Events

The definitions of an AE or SAE can be found in Section 10.2 (Appendix 2).

AE(s) will be reported by the patient (or, when appropriate, by a caregiver, surrogate, or the patient's legally authorized representative).

The investigator and any qualified designees are responsible for detecting, documenting, and recording events that meet the definition of an AE or SAE and remain responsible for following up AEs that are serious, considered related to the study drug or study procedures, or that caused the patient to discontinue the study (see Section 7).

8.3.1 Time Period and Frequency for Collecting Adverse Events and Serious Adverse Events Information

All AEs and SAEs will be collected from the time of the first study drug administration until Day 104. Medical occurrences that begin before the start of study drug but after obtaining informed consent will be recorded on the Medical History/Current Medical Conditions section of the CRF, not the AE section.

All SAEs will be recorded and reported to the sponsor or designee immediately and under no circumstance should this exceed 24 hours, as indicated in Section 10.2 (Appendix 2). The investigator will submit any updated SAE data to the sponsor within 24 hours of it being available.

The investigators are not obligated to actively seek AEs or SAEs after conclusion of the study participation. However, if the investigator learns of any SAE, including a death, at any time after a patient has been discharged from the study, and he/she considers the event to be reasonably related to the study drug or study participation, the investigator must promptly notify the sponsor.

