1.3 Schedule of Activities (SoA)

Table 1. Part	1 - Sche	dule	of A	ctivit	ies													
	-2ª						St	udy I)rug	Adm	inistr	atior	Per:	iod				Notes
	Screening D -28 to D -2	D -2ª	D-1ª	DIa	D2-6 ^a	D8	D9-13ª	D15a	D16-20ª	D22ª	D23-27a	D29a	D30-34ª	D36ª	D64ª	D104a	E/Db	
							Gene	ral a	nd Sa	ifety .	Asses	smei	ıts					
Informed consent	X																	*
Eligibility criteria	x		X								,				9 3			Recheck eligibility before randomization and/or first dose of study drug
Medical history ^c (includes substance usage)	х	Х	х															Medical occurrences that begin before the start of study drug but after obtaining informed consent will be recorded on the Medical History/Current Medical Conditions section of the CRF, not the AE section
Demography	X																	
Physical and neurological examination	x		X											X		X	X	Physical examination will include height (screening only) and weight measurements; see also Section 8.2.1
Randomization			X															

CONFIDENTIAL Page 20 of 101

Protocol TB006AD2102

Protocol Date and Version: 15 Oct 2021; v 3.0

Table 1. Part	1 - Sche	dule	of A	ctivit	ies													
	-2"						St	udy l	Drug	Adm	inisti	ation	ı Per	iod				Notes
	Screening D -28 to D -2	D -2a	D-1ª	D1ª	D2-6ª	BQ	D9-13ª	D15a	D16-20ª	D22ª	D23-27a	D29a	D30-34a	D36 a	D64ª	D104ª	E/D ^b	
Vital signs	X		х	х		X		X		X		X		X	X	X	x	Pre-dose, then 2 and 6 hours after the end of the study drug infusion on D1, D8, D15, D22, D29; otherwise once on the days indicated; see Section 8.2.2 for vital signs assessments
12-lead ECG	х		X	X		x		X		X		X		X	X	X	X	D1, D8, D15, D22, D29: pre-dose, then 2 and 6 hours after end of study drug infusion D-1, D36, D64, D104, E/D: time-matched with D1, D8, D15, D22, D29 pre-dose to the extent possible
AE monitoring				X	X	X	X	X	X	X	X	X	X	X	X	X	X	All AEs and SAEs will be collected from the time of the first study drug administration until D104.
Prior/concomitant medication review	X	X	X	X	X	X	X	X	X	X	X	X	X	X	X	X	X	
C-SSRS	X			X		X		X		X		X		X	X	X	X	

CONFIDENTIAL Page 21 of 101

Protocol TB006AD2102

Protocol Date and Version: 15 Oct 2021; v 3.0

Table 1. Part 1	- Sche	dule	of A	ctivit	ies													
	g -2ª						St	udy l	Drug	Adm	inistr	atior	ı Per	iod				Notes
	Screening D -28 to D -2	D -2ª	D-1ª	D1ª	D2-6ª	D8	D9-13ª	D15a	D16-20ª	D22ª	D23-27a	D29a	D30-34a	D36 a	D64ª	D104ª	E/D _b	

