Blood sample for ApoE4 genotyping	X																	Optional ApoE4 sampling is collected at screening but can be taken at any visit until the last study visit (Section 8.7)
					J	Phar	maco	kinet	ics ar	ıd Ph	arm	acody	ynam	ics				
Blood sample for ADA assessment				X		X								X		X		ADA assessment is performed on blood sample collected for PK assessments; D1 and D8 assessment is performed on the pre-dose sample
Lumbar puncture for CSF collection ^e			х											X				Lumbar puncture indicated for D-1 can be performed any time between D-8 and D-1 CSF biomarkers, and TB006 levels will be determined in CSF

AD = Alzheimer's Disease; ADA = anti-drug antibody; AE = adverse event; anti-HCV = hepatitis C virus antibody; ApoE4 = apolipoprotein E4; COVID = coronavirus disease; CRF = case report form; C-SSRS = Columbia Suicide Severity Rating Scale; CSF = cerebrospinal

fluid; D = Day; DSM-5 = Diagnostic and Statistical Manual of Mental Disorders, Fifth Edition; ECG = electrocardiogram; E/D = Early Discontinuation;

HBsAg = hepatitis B surface antigen; IgM anti-HBc = immunoglobulin M antibody to hepatitis B core antibody; IV = intravenous(ly); MMSE = Mini-Mental State Examination;

NINCDS-ADRDA = National Institute of Neurological and Communicative Disorders and Stroke –

Alzheimer's Disease and Related Disorders Association; NPI = Neuropsychiatric Inventory; PD = pharmacodynamic(s);

PK = pharmacokinetic(s); SAE = serious adverse event.

CONFIDENTIAL Page 24 of 101

a Visit days and procedures are allowed a window of \pm 2 days from Day 1 to End of Treatment.

Protocol TB006AD2102

Protocol Date and Version: 15 Oct 2021; v 3.0

b Applicable only for patients who discontinue early from the study.

- c The medical history assessed at the screening visit should include prior AD treatment assessment(s). Establishing the clinical diagnosis of AD should include use of criteria from the DSM-5 Criteria for Major Neurocognitive Disorder (previously dementia) (Section, 10.4, Appendix 4) and the NINCDS-ADRDA (Note: ADRDA is now the Alzheimer's Association) (Section 10.5, Appendix 5).
- d The Cognitive Drug Research battery is to be performed twice during the screening visit in both Part 1 and Part 2.
- e The lumbar puncture procedure is optional.

f

Protocol TB006AD2102

Protocol Date and Version: 15 Oct 2021; v 3.0

	.2a						St	udy I)rug	Adm	inistr	ation	Peri	iod				Notes

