5.4 Screen Failures

Screen failures are defined as patients who consent to participate in the clinical study but are not subsequently randomized. A minimal set of screen failure information is required to ensure transparent reporting of screen failure patients to meet the CONSORT publishing requirements and to respond to queries from regulatory authorities. Minimal information includes

Protocol TB006AD2102

Protocol Date and Version: 15 Oct 2021; v 3.0

demography, screen failure details, eligibility criteria, medical history, prior therapies, and any SAE.

Individuals who do not meet the criteria for participation in this study (screen failure) may be rescreened if they have the potential to be included. Rescreened patients should be assigned the same patient number as for the initial screening. Informed consent is required before patients can be rescreened. See Section 10.1.3 (Appendix 1) for Informed Consent Process details.

Protocol TB006AD2102

Protocol Date and Version: 15 Oct 2021; v 3.0

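### A serious complication of a study procedure before the first dose has no stated SAE route in patients who are later dosed, and the rule conflicts with the screen-failure section

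*Protocol*

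**What the plan says.** **Collection window.** Protocol 8.3.1 sets the start and end: "All AEs and SAEs will be collected from the time of the first study drug administration until" Day 104. The notes to both schedules in Protocol 1.3 give the same rule: "All AEs and SAEs will be collected from the time of the first study drug administration until D104". SAP 6.3 (safety reporting period) and SAP 12.1 (AE reporting period) also start at the first infusion on Day 1.

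**Earlier events.** Protocol 8.3.1 covers "Medical occurrences that begin before the start of study drug but after obtaining informed consent" and says that they "will be recorded on the Medical History/Current Medical Conditions section of the CRF, not the AE section". It makes no exception for seriousness or for a link to a study procedure.

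**Pre-dose procedures.** Screening runs from Day -28. In Part 1 the schedule adds a baseline CSF sample: "Lumbar puncture indicated for D-1 can be performed any time between D-8 and D-1". A footnote adds: "The lumbar puncture procedure is optional". Protocol 2.3.1 names bleeding, infection and herniation among the risks of lumbar puncture.

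**Texts that point the other way.** Protocol 8.3 asks investigators to follow up AEs that are, among other things, "considered related to the study drug or study procedures". Protocol 5.4 defines the minimum record for screen failures as "demography, screen failure details, eligibility criteria, medical history, prior therapies, and any SAE".

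**The concern.** Some study procedures, including one with recognized serious risks, are done before safety collection opens. If such a procedure causes serious harm and the patient is still dosed, the protocol treats the harm as part of the patient's history. The 24-hour report to the sponsor is not triggered, and nobody is asked to grade the event or judge its cause. What is at stake is oversight of procedure-related harm, not the estimate of the drug's effect. The same wording also leaves Section 5.4 asking for a kind of event that, under Section 8.3.1, a screen failure cannot have.

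**Working it through.** The plan has no figure to reproduce here. The check compares time windows, then definitions, then the routes open to each kind of patient.

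**1. Windows.** Collection runs from Day 1 to Day 104. The baseline lumbar puncture may take place from Day -8 to Day -1. The study-day formulas in SAP 9.1 have no Day 0, so Day -1 is the day before first dose. The overlap is 0 days. The second lumbar puncture, on Day 36, lies inside the window (1 ≤ 36 ≤ 104). A complication of the same procedure is thus an AE after Day 36 but medical history before Day 1. For all other procedures after consent, the uncovered period can start as early as Day -28.

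**2. Definitions.** Protocol 10.2.1 defines an AE as an occurrence associated in time with use of study drug. Before first dose there has been no such use. Protocol 10.2.2 adds that an event which is not an AE cannot be an SAE, however serious. The 24-hour duty in 8.3.1 applies to SAEs, so it does not reach a pre-dose event. The attributes that Protocol 10.2.3 requires (severity, relatedness, action taken) apply to AEs, so they are not required either.

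**3. Routes by patient.**

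| Patient with a serious procedure complication before Day 1 | Stated record | Stated 24-hour report |
|---|---|---|
| Later dosed | Medical history; an AE only if first detected after dosing (10.2.1) | None |
| Not randomized (screen failure) | SAE required by 5.4, but excluded by 8.3.1 and 10.2.2 | None that is consistent with 8.3.1 |
| Randomized, then not dosed | Medical history; not a screen failure under 5.4 | None |

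**4. The other end of the study.** After a patient leaves the study, 8.3.1 still requires prompt notification of an SAE that the investigator thinks reasonably related to study participation. No matching duty exists before first dose.

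**5. Size.** Part 1 plans 3 groups × 8 patients = 24 randomized. That is a ceiling on randomized patients who have the baseline puncture, because the procedure is optional. Replacements, and patients punctured but never randomized, would add to it. The documents give neither uptake nor a complication rate, so no expected number of events can be calculated.

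**6. Analysis.** Protocol 9.4.2.1 treats every AE as treatment emergent because collection starts at first dose. SAP 12.1 limits tables to treatment-emergent events and lists all AEs. A separate listing of pre-dose events would therefore change no planned treatment-emergent table.

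**The case against.** Starting at first dose is a deliberate rule, repeated in 8.3.1, both schedules, 9.4.2.1 and the SAP. It changes no efficacy or treatment-emergent result. That is correct, and it is why the point is minor.

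A reader might go further in four ways that the documents do not support.

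- **That SAEs are not collected at all before dosing.** Section 5.4 asks for them in screen failures. Eligibility is rechecked on Day -1, so a patient with serious harm before randomization could well become one.
- **That the event would be absent from the safety data or hidden from the sponsor.** It is entered in the CRF as medical history, and SAP 10.3 lists and tabulates medical history for dosed patients. Protocol Section 8 wants immediate safety concerns raised with the sponsor at once, and 10.1.1 has the investigator notify the IRB/IEC of significant safety findings. These give partial cover. Neither sets a 24-hour sponsor report for such an event, and the Section 8 text is framed around whether study drug should continue.
- **That Section 8.3 contradicts 8.3.1.** Its mention of study procedures is satisfied by procedures inside the window, such as the Day 36 lumbar puncture and later blood draws. The real conflict is with 5.4.
- **That Day -8 to Day -1 is the whole gap.** That window belongs to the lumbar puncture alone.

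**Conclusion.** The point holds as a minor safety-reporting gap and an internal inconsistency. For a patient who goes on to be dosed, a serious complication of a pre-dose procedure has no stated 24-hour sponsor report and no severity or causality assessment. It is kept only as medical history unless first detected after dosing. Sections 5.4 and 8.3.1 cannot both be followed for screen failures; this applies in both parts and does not depend on lumbar puncture.

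The lumbar puncture example concerns about 24 randomized patients at most, all in Part 1. The treatment comparison is unaffected.

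The conclusion assumes that sites and the CRF follow the protocol as written. The eCRF specification cited in the SAP was not available and could already provide for pre-dose SAEs.

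**What to change.** Collect and report SAEs and study-procedure-related AEs from informed consent. Changing 8.3.1 alone would not do this, because the definitions would still exclude the events. The edits needed are:

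- **Protocol 5.4, 8.3.1, 10.2.1 and 10.2.2:** one common start point, and AE and SAE definitions that admit an event caused by a study procedure before first dose.
- **Protocol 10.2.3:** relatedness to a study procedure as an attribute, since the present text asks about study drug and other required therapies.
- **Protocol 1.3 (Tables 1 and 2) and 9.4.2.1:** matching start of collection, and removal of the statement that every AE is treatment emergent.
- **SAP 6.3, 12.1 and Appendix I (Tables 5 and 6):** matching periods, a separate listing of pre-dose events, and treatment-emergent tables still starting at first dose.

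Pre-dose events should carry complete onset dates. Under SAP 9.4.1, a start date that lacks the day and falls in the month of first dose is set to the date of first dose, which would move the event into the treatment-emergent tables.

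The cost is these text edits, opening the AE form at consent, and a little extra data collection before dosing.

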8.3.2 Method of Detecting Adverse Events and Serious Adverse Events

The method of recording, evaluating, and assessing causality of AEs and SAEs and the procedures for completing and transmitting SAE reports are provided in Section 10.2 (Appendix 2).

Care will be taken not to introduce bias when detecting AEs and/or SAEs. Open-ended and non-leading verbal questioning of the patient is the preferred method to inquire about AE occurrences.

Protocol TB006AD2102

Protocol Date and Version: 15 Oct 2021; v 3.0

8.3.3 Follow-up of Adverse Events and Serious Adverse Events

After the initial AE/SAE report, the investigator is required to proactively follow each patient at subsequent visits/contacts. All SAEs will be followed until resolution, stabilization, the event is otherwise explained, or the patient is lost to follow-up (as defined in Section 7.3). Further information on follow-up procedures is given in Section 10.2 (Appendix 2).

8.3.4 Regulatory Reporting Requirements for Serious Adverse Events

- Notification by the investigator to the sponsor of an SAE is essential so that legal obligations and ethical responsibilities towards the safety of patients and the safety of a study drug under clinical investigation are met.
- The sponsor has a legal responsibility to notify the FDA about new safety information of a study drug under clinical investigation. The sponsor will comply with regulatory requirements relating to safety reporting to the FDA, IRB/IEC, and investigators.
- Investigator safety reports must be prepared for SUSARs according to local regulatory requirements and sponsor policy and forwarded to investigators as necessary.
- An investigator who receives an investigator safety report describing an SAE or other specific safety information (eg, summary or listing of SAEs) from the sponsor will review and then file it along with the IB and will notify the IRB/IEC, if appropriate according to local requirements.

8.3.5 Disease-related Events and/or Disease-related Outcomes not Qualifying as Adverse Events or Serious Adverse Events

The following DREs are common in patients with AD and can be serious/life threatening:

- Anxiety and psychosis
- Dysphagia and other eating disorders
- Exacerbation of AD
- Injuries from falls

Because these events are typically associated with the disease under study, they will not be reported according to the standard process for expedited reporting of SAEs even though the event may meet the definition of an SAE. These events will be recorded in the patient's CRF when reported. These DREs will be monitored by the SRC on a routine basis.

NOTE: However, if either of the following conditions applies, then the event must be recorded and reported as an SAE (instead of a DRE):

• The event is, in the investigator's opinion, of greater severity, frequency, or duration than expected for the individual patient.

OR

Protocol TB006AD2102

Protocol Date and Version: 15 Oct 2021; v 3.0

• The investigator considers that there is a reasonable possibility that the event was related to study drug.

8.4 Treatment of Overdose

For this study, any dose of study drug greater than the planned doses of study drug indicated in this protocol, will be considered an overdose. There is no recommendation for a specific treatment for an overdose.

In the event of an overdose, the investigator should:

- Contact the Medical/Scientific Monitor immediately.
- Closely monitor the patient for any AE/SAE and laboratory abnormalities until TB006 can no longer be detected systemically until the next scheduled dose.
- Obtain a plasma sample for PK analysis according to the protocol schedule unless otherwise advised by the Medical/Scientific Monitor.
- Document the quantity of the excess dose as well as the duration of the overdose in the CRF.

Decisions regarding dose interruptions or modifications will be made by the investigator in consultation with the Medical/Scientific Monitor based on the clinical evaluation of the patient.

8.5 Pharmacokinetics

- Whole blood samples of approximately 5 mL will be collected for measurement of
 plasma concentrations of TB006 as specified in the SoA (Table 1 and Table 2).
 Additional samples may be collected at additional time points during the study if
 warranted and agreed upon between the investigator and the sponsor. The timing of
 sampling may be altered during the course of the study based on newly available data (eg,
 to obtain data closer to the time of peak plasma concentrations) to ensure appropriate
 monitoring.
- Instructions for the collection and handling of biological samples will be provided by the sponsor. The actual date and time (24-hour clock time) of each sample will be recorded.
- Samples will be used to evaluate the PK of TB006. Each plasma sample will be divided into 2 aliquots (1 each for PK and a back-up). Samples collected for analyses of plasma TB006 concentration may also be used to evaluate safety or efficacy aspects related to concerns arising during or after the study.
- Other than ApoE4 genetic testing from a sample at the Screening visit, genetic analyses will not be performed on these plasma samples. Patient confidentiality will be maintained. At visits during which whole blood samples for the determination of multiple aspects of TB006 will be taken, 1 sample of sufficient volume can be used.

Protocol TB006AD2102

Protocol Date and Version: 15 Oct 2021; v 3.0

• Lumbar puncture procedure will be performed at the time points as specified in the SoA (Part 1 only) (Table 1) to obtain CSF samples for measurement of concentrations of TB006. The lumbar procedure is optional for participating patients.

Drug concentration information that would unblind the study will not be reported to investigative sites or blinded personnel until the study has been unblinded.

Any changes in the timing or addition of time points for any planned study assessments must be documented and approved by the relevant study team member and then archived in the sponsor and site study files but will not constitute a protocol amendment. The IRB/IEC will be informed of any safety issues that require alteration of the safety monitoring scheme or amendment of the ICF.

8.6 Pharmacodynamics

8.6.1 Blood Samples for Biomarker Assessments

Venous blood samples of approximately 5 mL will be collected for measurement of plasma, and other relevant biomarkers at the time points specified in the SoA (Table 1 and Table 2).

8.6.2 Lumbar Puncture (Part 1 only)

Lumbar puncture procedure (optional for participating patients) will be performed at the time points as specified in the SoA (Table 1) to obtain CSF samples for measurement of and other relevant biomarkers.

8.6.3 Cognition Testing

Patients will perform a battery of cognition tests, including the MMSE, the Clinical Dementia Rating Scale, the Cognitive Drug Research system battery, and the NPI throughout the study to assess cognition. Tests, with the exception of the Cognitive Drug Research system battery will be performed by paper only. The Cognitive Drug Research system battery will be performed using an electronic device.

